## **Methods:**

### Overview of design:

A randomized, open, blank controlled, single-center clinical trial was conducted to compare the survival benefits of statins in breast cancer patients with dyslipidemia (low and medium risk of ASCVD). The control group used dietary intervention instead of statins. The main endpoint was 5 years DFS. The subjects were breast cancer patients. In this study, 348 patients were randomly divided into two groups according to patients' wishes and written informed consent. The experimental group: control group = 1:1. Subjects were screened and administered continuously until the disease progressed and the toxicity was intolerable. Informed consent was withdrawn or the researcher decided that the drug must be discontinued.

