8) Other serious diseases, including:

Congestive heart failure (NYHA grade II, III, IV); dyspnea at rest or requiring oxygen therapy; severe infection; uncontrolled diabetes mellitus;

9) If there are serious mental or mental disorders, it is estimated that the subjects' compliance to participate in this study is not strong.

10) Drug allergies to research drugs are known.

11) Participated in other drug clinical trials in the past 30 days.

12) Failure to complete at least one cycle of clinical trials based on this protocol, and failure to evaluate safety and effectiveness.

13) Serious violation of this study program, not in accordance with the prescribed dose, method and course of treatment.

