#### Plans for sampling, recruiting and retaining subjects:

- Sample type: Convenience sample
- Sampling procedures: Convenience sampling will be used to enroll a cohort of breast cancer patients with dyslipidemia (low and medium risk of ASCVD), and randomly separate them into two groups. We prepare to use SPSS software to do the randomly separation. Experimental group used statins, the other one used dietary intervention instead of statins.
- Recruitment method: When patients presented our hospital diagnosed of breast cancer with dyslipidemia (low and medium risk of ASCVD), we will review these patients' medical records to find out the potential subjects for this study according to the inclusion and exclusion criteria. The eligible subject who is willing to participate in this study will be enrolled and consented. They will be randomly (using SPSS software) divided into 2 groups. One is statins group, the other one is control group.

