#### Measurements:

- Predictor variables:

The predictor variable we are assessing is whether use statins. According to which, we established the intervention group and control group.

- Outcome variables:

The primary outcome: DFS (disease free survival) rate

Secondary outcome: OS (overall survival) rate

- Potential confounders:

Since this protocol is an RCT (randomly clinical trial) on survival benefits between statins group and control group, it will balance the confoundings in it, such as age, slight pathology difference, tumor size difference, lymph node status difference, tumor grade difference, and the different surgeons between the 2 groups.

- Plans for randomization, blinding, run-in period as needed:

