#### 1) Randomization

We prepare to use SPSS software to do the randomly separation. According to the inclusions and exclusions, once we find the right patient, we will put the name in computer. The computer will randomly tell which group the patient will be in. After explanations to the patients, and receiving the patient agreements, we will sign the informed consent with them.

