#### 3) Run-in design

We would like to recruit patients from the breast surgery department. Clinic doctors in this department will help us to find appropriate patients. Then appraiser will do the diagnostic evaluation. If patients meet the included standard, we will ask them to sign informed consent and the registration form (questionnaire). Meanwhile we will make a calendar for their treatment and supervision.

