#### **Statistical issues:**

### Primary outcomes:

The research question is whether statins can benefit breast cancer patients with dyslipidemia (low and medium risk of ASCVD). The main endpoint was DFS. A review of the literature suggests that simvastatin reduced the recurrence rate of breast cancer by 10%. The investigator would like to be able to detect a difference of 10% or more in DFS change between the two groups. How many patients are required in each group at  $\alpha$  (two-sided) = 0.05;  $\beta$  = 0.10, power = 0.90.

1. Null Hypothesis: For breast cancer patients with dyslipidemia (low and medium risk of ASCVD) under endocrine therapy, whether statin used is the same in DFS.
2. Alternative Hypothesis (two-sided): For breast cancer patients with dyslipidemia (low and medium risk of ASCVD) under endocrine therapy, whether statin used is different in DFS.
3. Effect size=0.1(10%\*2)
4. Standard deviation of CTC=1
5. Standardized effect size=effect size/standard deviation=0.1/1=0.1
6.  $\alpha$  (two-sided) = 0.05;  $\beta$  = 0.10, power = 0.9
7. Based on Appendix 6A from the text book, the estimated sample size is 157 in each group.
8. Ultimate sample size =  $2*157/0.9= 348$

Looking across from a standardized effect size of 0.10 in the leftmost column in Table 6A and down from  $\alpha$  (two-side) =0.05 and  $\beta$  = 0.10 is the required sample size of 157patients in statins group and control group. With 10% dropout the final sample size is 348[14].

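### Exclusion criteria 12 and 13 can only be met after randomisation, and no all-randomised analysis set keeps those patients in the DFS comparison

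*Combined protocol and SAP*

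**What the plan says.** The list of exclusion criteria under Study subjects ends with two items that differ in kind from the rest. Number 12 is "Failure to complete at least one cycle of clinical trials based on this protocol, and failure to evaluate safety and effectiveness". Number 13 is "Serious violation of this study program, not in accordance with the prescribed dose, method and course of treatment".

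The Recruitment method paragraph checks medical records against the criteria, enrols and consents eligible patients, and then allocates them: "They will be randomly (using SPSS software) divided into 2 groups". The Randomization paragraph likewise allocates once a suitable patient is found: "The computer will randomly tell which group the patient will be in". The paragraph headed Run-in design covers recruitment, diagnostic evaluation, consent and a visit calendar ("If patients meet the included standard, we will ask them to sign informed consent and the registration form (questionnaire"). It describes no treatment before allocation.

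On analysis, the Abstract names a t-test, Kaplan-Meier curves and a log-rank test without saying which patients enter them. Under Measurements, the comparison variable is given as follows: "The predictor variable we are assessing is whether use statins". No intention-to-treat, full-analysis or per-protocol set is defined. The only attrition figure is the 10% dropout allowance in the sample-size section.

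**The concern.** Eligibility should be settled from what is known before allocation. Completing a cycle, being evaluable and following the assigned treatment are all known only afterwards, and all may depend on the arm and on prognosis. If patients are removed on these grounds, those left are no longer the groups that randomisation made comparable. The Measurements section relies on that comparability to balance age, tumour size, nodal status and grade.

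Unequal removal is plausible. Only the statin arm has a study drug with a prescribed dose. The Overview of design describes the trial as open ("A randomized, open, blank controlled, single-center clinical trial was conducted"), so what counts as a serious violation may be judged with the arm known; the Blinding paragraph says otherwise, and the two need reconciling. The direction is still not fixed. Controls can depart from the method and course of the dietary intervention. The Overview of design also lets treatment stop for toxicity, and Ethical considerations lets dosage be adjusted. How either relates to criterion 13 is not stated and must be reconciled.

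**Working it through.** **Plan's own figures.** The sample-size section inflates 157 per group for 10% dropout: 2 × 157 / 0.9 = 348.9, given as 348, so 348 / 2 = 174 per arm. (The 157 does not follow from the stated standardised effect of 0.10, two-sided α of 0.05 and 90% power, which give 2,102 per group. That is a separate matter and does not affect this point.) The difference the trial aims to detect is 10 percentage points of DFS.

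**Timing.** Both criteria refer to conduct under this protocol. Protocol treatment starts after allocation and there is no run-in treatment. Applied at screening, the criteria exclude nobody; they can act only on randomised patients.

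**Possible size.** Assumed, because the documents give no such rates: no true statin effect; 5 years of follow-up for everyone; 5-year event risk R of 10%, 20% or 30% in each randomised arm. A fraction f of an arm is removed, and those removed have k times the event risk of those who stay. The 10% removal borrows the dropout figure, which is a different concept; the 20% is purely illustrative.

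Since R = (1 − f) × r + f × k × r, the risk among those who stay is r = R / (1 − f + k f). The spurious DFS difference is control r minus statin r, with + favouring statins.

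Example: R = 0.20, f = 0.10 in the statin arm only, k = 2. Then r = 0.20 / 1.10 = 0.1818, and 0.20 − 0.1818 = +1.8 points.

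Type I error comes from 20,000 simulated trials per scenario (exponential DFS among those who stay, censoring at 5 years, two-sided log-rank test at 0.05, 174 per arm before removal).

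| Removed, statin / control | k | DFS shift in points, R = 10 / 20 / 30% | Type I error |
|---|---|---|---|
| 10% / 0 | 0.5 | −0.5 / −1.1 / −1.6 | 5.2 / 5.8 / 6.0% |
| 10% / 0 | 1 | 0 | about 5% |
| 10% / 0 | 2 | +0.9 / +1.8 / +2.7 | 5.9 / 6.7 / 8.6% |
| 10% / 0 | 3 | +1.7 / +3.3 / +5.0 | 7.9 / 12.3 / 17.3% |
| 10% / 10% | 2 | 0 | about 5% |
| 10% / 20% | 2 | −0.8 / −1.5 / −2.3 | 5.9 / 6.1 / 7.3% |
| 20% / 10% | 2 | +0.8 / +1.5 / +2.3 | 5.4 / 6.4 / 6.9% |
| 0 / 10% | 3 | −1.7 / −3.3 / −5.0 | 7.9 / 11.7 / 17.5% |

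**Cross-check.** A two-proportion normal approximation, with 80% DFS in both arms, 10% of the statin arm removed and 50% DFS among those removed, gives (0.80 − 0.10 × 0.50) / 0.90 = 0.833. That is a shift of +3.3 points, with type I error of 12.1%. It is the R = 20%, k = 3 case, and it agrees with the simulated 12.3%.

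**Smaller removal.** With 5% of one arm removed at k = 2, r = R / 1.05 and the shift is 0.5 / 1.0 / 1.4 points, with type I error of 5.1 / 5.4 / 5.2% (4,000 simulated trials). With 2% removed, r = R / 1.02 and the shift is 0.2 / 0.4 / 0.6 points.

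**The case against.** The strongest reply is that the documents state only one use of the exclusion criteria, at screening, where 12 and 13 exclude nobody. They may be inert text or rules for stopping treatment. The sentence after the definition of the comparison variable says the two groups were established on that basis, and elsewhere the groups are formed by randomisation, which leans towards comparing patients as allocated.

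This stands in part. No sentence says that a randomised patient who meets 12 or 13 is dropped from the DFS analysis, so bias is possible rather than certain. But the milder reading is not stated either. Criterion 12 speaks of evaluating safety and effectiveness, which points to analysis. Comparing groups as allocated does not settle who is kept in them.

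A second objection concerns size, and it is fair. Every rate is assumed. The 5.0-point extreme needs a 30% event risk, removal from one arm only, and 75% events among those removed against 25% among those kept. Criterion 12 requires both non-completion and non-evaluability, and criterion 13 a serious violation, so removal could well be below 10% and the shift small. Five years of follow-up for all is also generous, because the Abstract gives the whole trial five calendar years including recruitment. These points limit the size; they do not remove the fault.

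**Conclusion.** The concern holds. The plan lists as exclusions two events that can occur only after allocation, and defines no analysis set to override them. Followed as written, it permits post-randomisation selection in the primary comparison.

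Under the assumptions shown, the spurious DFS difference runs from −5.0 to +5.0 points, at most half of the 10-point target. It is around 1 point with 5% one-sided removal at twice the risk, and zero when removal is equal in both arms with similar prognosis or unrelated to prognosis. Neither the sign nor the size can be known in advance from the documents. The fault must be corrected before outcomes are examined, because choosing the analysis set afterwards would itself weaken the result.

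**What to change.** Delete items 12 and 13 from the exclusion criteria and add to the statistical section:

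> The primary DFS analysis includes all randomised patients in the group to which they were allocated, counted from randomisation, regardless of treatment received. DFS follow-up continues on the existing visit form after study treatment stops.

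Use the two criteria at most to define a supportive per-protocol set, and report the number of patients meeting each, with reasons, by arm.

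Two matters need attention alongside. The Randomization paragraph describes allocation before consent is signed, whereas the Abstract and Recruitment method put consent first; this must be reconciled so that the all-randomised set contains only consented patients. The appendix form schedules visits to 5 years but has no recurrence field at 1 and 3 months or at 2.5, 3.5 and 4.5 years, so recurrence dates should be captured at the next visit that has one.

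The cost is wording, with no new visits. The statistical downside is dilution by non-adherence: if, by assumption, 10% of the statin arm gained nothing, a true 10-point difference would appear as about 0.9 × 10 = 9 points.

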Based on current epidemiological and clinical studies, it is practical and reasonable to set appropriate cholesterol-lowering target values according to patients' overall cardiovascular risk level. For low, medium and high risk patients without ASCVD, the LDL\_C target values recommended by the guidelines for prevention and treatment of adult dyslipidemia in China are < 4.1, 3.4 and 2.6 mmol/L, respectively (corresponding non-HDL\_C target values are LDL\_C + 0.8 mmol/L, cholesterol conversion unit: 1 mmol/L = 1 mg/dl \* 0.0259), beyond which lifestyle interventions and (or) drug therapy should be initiated. These suggestions are based on the epidemiological characteristics of dyslipidemia in Chinese residents and the available clinical evidence, which are the basic criteria for current lipid management. Based on cholesterol theory and many new research results published in recent years, it is possible to further reduce the cardiovascular risk of patients by continuing to reduce LDL\_C or non-HDL\_C levels to a certain extent. At present, the target of blood lipid intervention for breast cancer patients lacks evidence-based medical support. Therefore, the Chinese consensus recommends that cholesterol [9] be controlled more strictly for postmenopausal women, referring to the expert recommendations of the prevention and treatment of dyslipidemia in the 2014 China Cholesterol Education Program. It is suggested that the ideal level of LDL\_C in postmenopausal breast cancer patients without risk factors should be < 3.4 mmol/L.

However, the consensus of Chinese experts on the management of dyslipidemia in early postmenopausal breast cancer published in 2017 has not made clear recommendations on which patients should use lipid-lowering drugs and how much to use. Especially in clinical practice, the control of blood lipid is a grey area for low-risk patients with ASCVD. In recent years, studies have shown that statins can reduce the recurrence and metastasis of breast cancer and improve the overall survival of breast cancer patients [10-13]. Therefore, this study is an active effort to seek a survival benefit program for patients at low and medium risk of ASCVD.

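### Exclusion items 12 and 13 can be judged only after randomisation; with no analysis set defined, applying them can bias the DFS and OS comparison in an unknown direction

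*Combined protocol and SAP*

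**What the plan says.** Under Study subjects, exclusion item 12 is "Failure to complete at least one cycle of clinical trials based on this protocol, and failure to evaluate safety and effectiveness" and item 13 is "Serious violation of this study program, not in accordance with the prescribed dose, method and course of treatment". They stand in the same list as ordinary entry conditions such as pregnancy or liver disease. Neither names an arm. The protocol does not define a cycle or say what makes a violation serious.

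The Overview of design describes the trial as open ("A randomized, open, blank controlled, single-center clinical trial was conducted") and sets the comparator: "The control group used dietary intervention instead of statins". The Blinding section says that patients and clinicians will not know the intention behind the grouping, but no placebo is described. On duration the Overview says: "Subjects were screened and administered continuously until the disease progressed and the toxicity was intolerable". It adds: "Informed consent was withdrawn or the researcher decided that the drug must be discontinued".

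On analysis, the Abstract names a t-test, and a log-rank test with Kaplan-Meier curves. No section names an analysis population, says that patients are analysed as randomised, or says whether a patient caught by item 12 or 13 is deleted, censored or kept. Measurements defines the predictor by statin use, not by assignment, and the hypotheses under Statistical issues do the same.

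**The concern.** A condition that can be checked only after treatment starts cannot work as an entry criterion. The natural way to apply it is to remove the patient after randomisation. The Potential confounders text relies on randomisation to balance age, tumour size, nodal status and grade, and that balance is secured only for everyone randomised.

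Two kinds of patient are exposed to item 13.

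- **A control who starts a statin** departs from her assigned method. Such starts are foreseeable. All patients have dyslipidemia, the Appendix form records lipids and statin use at 12 follow-up visits, and the Significance section gives LDL-C targets "beyond which lifestyle interventions and (or) drug therapy should be initiated". There is no rescue rule for controls.
- **A statin patient who skips, changes or stops her drug** for a reason that the Overview does not list also departs from it.

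Because the trial is open, whether a departure is serious can be decided with the arm known. Because study treatment runs until progression, a patient can depart from it only while event-free. Deleting her takes an event-free patient out of her arm and raises that arm's apparent event risk. If deletions are unequal, or linked to prognosis, the primary and secondary comparisons are no longer the randomised ones.

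**Working it through.** The plan gives no figure for removals, statin starts in controls or control-arm DFS, so there is no stated result to reproduce. Two plan figures are used: 348 patients randomised 1:1, so 348/2 = 174 per arm, and the 10-point DFS target under Primary outcomes. Everything else is assumed.

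**1. Deletion in controls only, no true statin effect.** Assume a 5-year event risk R = 20%, a share s = 5, 10 or 20% of event-free controls starting a statin by year 5, constant hazards, starts unrelated to prognosis, full 5-year follow-up, and no deletions in the statin arm.

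With l = -ln(1-R) and g = -ln(1-s):

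- event before start: A = l/(l+g) × (1 - exp(-(l+g)))
- start before event: B = g/(l+g) × (1 - exp(-(l+g)))
- control risk after deletion = A/(1-B)

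For s = 20%, l = g and 1 - 0.8 × 0.8 = 0.36, so A = B = 0.18 and the control risk reads 0.18/0.82 = 21.95%. The last two columns come from log-rank simulation with 20,000 runs (simulation standard error 0.1 to 0.2 points).

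| s | Removed of 174 | Control risk reads | Spurious benefit (points) | False 'statin better' | Two-sided error |
|---|---|---|---|---|---|
| 5% | 7.8 | 20.43% | 0.43 | 3.1% | 4.9% |
| 10% | 15.6 | 20.90% | 0.90 | 4.3% | 5.9% |
| 20% | 31.3 | 21.95% | 1.95 | 6.6% | 7.5% |

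At s = 20%, R = 10% gives 11.09% (1.09 points; false 'statin better' 5.0%) and R = 30% gives 32.58% (2.58 points; 7.7%).

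**2. Same model, other ways of applying the rule (R = 20%).**

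- All kept as randomised, or censored at the start date: false 'statin better' 2.4 to 2.7%, so no inflation.
- Entry spread evenly over the 5-year study period in the Abstract: 2.8, 3.2 and 4.1% for s = 5, 10 and 20%.
- 10% deleted in both arms: 2.4 to 2.7%, so no bias.
- 20% deleted in controls, 10% in the statin arm: 3.9%.
- 10% in controls, 20% in the statin arm: 'statin better' 1.3%, 'statin worse' 4.4%.
- 10% in controls, 30% in the statin arm: 0.7% and 7.4%.

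**3. Prognosis and timing.** A simulation of 2,000,000 patients per arm, again with no true effect, varied 5-year DFS (70 to 90%), the share prone to deviate (10 to 30%), the timing (first 3 months, or spread over 5 years) and the hazard of prone patients relative to others (0.7 to 2.0). The shift in the statin-minus-control DFS difference was:

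- controls only, equal prognosis, starts spread out: +0.5 to +4.4 points
- controls only, equal prognosis, early starts: 0.0 to +0.3
- controls only, starters at hazard ratio 1.5 to 2.0, early starts: -0.4 to -5.1
- controls only, the same hazard ratios, starts spread out: +0.1 to +2.7
- controls only, all cases: -5.1 to +6.0
- deletion in both arms, all cases run: -1.8 to +1.3

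Keeping all randomised patients gives a shift of 0 in every case.

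**The case against.** A reader might infer that the rule tilts DFS toward statins, because the Overview lists reasons to stop the drug and none for a control to start one. The documents do not support that direction. Item 13 names no arm, and its reference to dose fits the statin arm at least as well as a diet arm. The listed stops do not cover ordinary non-adherence over years of treatment. The event-free mechanism works the same way in whichever arm loses patients, and steps 2 and 3 show the sign vanishing or reversing.

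Other objections carry weight against the size:

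- The figures in step 1 need an eligibility item to act as removal after randomisation, removal to mean deletion and not censoring, every control start to count as serious, and only controls to be affected. None of this is stated.
- The Abstract puts the whole study between March 2019 and March 2024, so full 5-year follow-up for every patient is the favourable case for the concern.
- The background passage on LDL-C targets lists lifestyle change among the responses and calls lipid control in low-risk patients a grey area. LDL-C above 4.9 mmol/L is excluded. How often controls would start a statin is unknown.

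These points remove the claimed direction and limit the magnitude. They do not change the fact that two listed exclusions depend on events after randomisation, with nothing in the plan to keep those patients in the analysis.

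**Conclusion.** The point holds as a rule that can give a wrong result, and not merely as missing detail. Items 12 and 13, applied as exclusions, remove randomised patients from either arm, and the resulting bias in DFS and OS has no fixed sign. It may favour statins if mainly event-free controls who start a statin are deleted. It may go against statins if more statin patients are deleted, or if control starters have a worse prognosis and start early. It is about nil if losses are equal and unrelated to prognosis, or if patients are censored at a deviation unrelated to prognosis.

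The step 1 figures describe one scenario and do not estimate what will happen. Small amounts of deletion matter little: at 5% starts the two-sided error is 4.9%. The change should be made because it is cheap and the bias, once introduced, could not be signed or corrected from what the plan specifies. Confidence is medium, since the protocol does not say how the items would be applied.

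**What to change.** 1. Delete items 12 and 13 from the exclusion list, or limit them to stopping study treatment, with follow-up for DFS and OS continued.
2. Add to Statistical issues: all randomised patients are analysed in their assigned arm for DFS and OS; a control who starts a statin stays in the control arm, and a statin patient who stops stays in the statin arm.
3. Report statin starts in controls, and statin stops, by arm, from the statin field already on the Appendix form.
4. Label any per-protocol result a sensitivity analysis, and censor at the date of the start or stop instead of deleting the patient.

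The cost is two items reworded and a few sentences added, with no new visits, tests or form fields.

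The trade-off is dilution of a real effect by crossover and non-adherence. With assumed event risks of 20% v 10% (hazard ratio ln 0.9/ln 0.8 = 0.47), 174 per arm and 10,000 log-rank runs, power without starts is 75.6%. Keeping control starters gives 73.2, 71.1 and 67.5% at 5, 10 and 20% starts, as the 10-point difference shrinks to 9.8, 9.5 and 9.0 points. Deleting them shows 77.4, 79.2 and 84.0%, but part of that gain is the same artefact that raises the false-positive rate in step 1.
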